#### **5.2.3 Prior and Concomitant Therapy**

Any medication or vaccine (including over-the-counter or prescription medicines, vitamins and/or herbal supplements) that the subject is receiving from 2 weeks prior to enrollment through 30 days post-dosing, must be recorded along with the reason for use, date(s) of administration including start and end dates, and dosage information including dose, route and frequency.

During the Post-Treatment Period, all medications taken will be recorded until 30 days following the last dose of study drugs. Only medications taken for SAEs assessed as related to the study drugs and treatment of HCV will be recorded thereafter.

The AbbVie Therapeutic Area Medical Director should be contacted if there are any questions regarding concomitant or prior therapies.

### **5.2.3.1 Prior HCV Therapy**

Part 1 will include only subjects that are treatment-naïve. For Part 2, prior or current use of any investigational or commercially available anti-HCV agents other than IFN, pegIFN or RBV, including telaprevir, boceprevir, sofosbuvir, ombitasvir, dasabuvir, paritaprevir, ledipasvir, daclatasvir, simeprevir, elbasvir, grazoprevir or an investigational DAA excludes a subject from this study. Subjects who previously participated in trials of investigational anti-HCV agents may be enrolled if they can produce documentation that they received only placebo.

Treatment experienced subjects must have discontinued previous therapy at least 6 months prior to the Screening Visit in order to be eligible for the study.

### **5.2.3.2 Concomitant Therapy**

Subjects must be able to safely discontinue any prohibited medications within 2 weeks or 10 half-lives of the medication, whichever is longer, prior to initial study drug administration and through 2 weeks following discontinuation of study drugs. Parent(s)/legal guardian(s) and the pediatric subject must review and sign the informed consent and assent respectively prior to discontinuing any prohibited medications for the purpose of meeting study enrollment criteria.

The investigator or a qualified designee should confirm that a concomitant medication can be safely administered with DAAs (including ritonavir) and RBV (if applicable). Some medications may require dose adjustments due to potential for drug-drug interactions.

The investigator or qualified designee should review concomitant medication(s) label(s), the locally approved labels for ombitasvir, paritaprevir, ritonavir, dasabuvir (if applicable) and ribavirin (if applicable) and <http://www.hep-druginteractions.org/> to screen concomitant medications at each visit for potential drug-drug interactions (DDI) with study drugs. Additionally, the site should document their DDI review in the subject's source.

Subjects using systemic ethinyl estradiol-containing contraceptive therapy have a higher risk for elevated ALT levels. Subjects using these kinds of medications must discontinue them at least 2 weeks prior to initial study drug administration. Subjects may replace the systemic ethinyl estradiol-containing contraceptive with a highly effective progestin-only hormonal contraceptive method or with another highly effective contraceptive method.

During the Post-Treatment Period, investigators should reassess concomitant medications. Subjects may resume previously prohibited medications or revert to pre-study doses, at a minimum of 2 weeks following discontinuation of study drugs, if applicable.

### **5.2.3.3 Prohibited Therapy**

In addition to the medications listed in [Table 7](#), use of known strong or moderate inducers of CYP3A (for GT1 and GT4 subjects receiving OBV/PTV/RTV with or without DSV), or strong inducers and inhibitors of CYP2C8 (only for GT1 subjects receiving OBV/PTV/RTV with DSV) are prohibited within 2 weeks or 10 half-lives of the medication, whichever is longer, prior to the initial dose of study drugs and through the first 2 weeks after the subject has completed study drugs in the Treatment Period.

Subjects must be able to safely discontinue any prohibited medications. Subjects must be consented prior to discontinuing any prohibited medications for the purpose of meeting study enrollment criteria. During the Post-Treatment Periods of Part 1 and Part 2, investigators should reassess prohibited medications and subjects may resume previously prohibited medications or revert to pre-study doses, at a minimum of 2 weeks following discontinuation of study drugs, if applicable.

#### **5.2.4 Contraception Recommendations and Pregnancy Testing**

The contraception recommendations in this paragraph are summarized in relation to the potential risk of the investigational products used in this study. All female subjects who are experiencing menses or are nearing sexual maturation in the opinion of the Principal Investigator, or who are of child-bearing potential should undergo pregnancy testing according to Section 5.3.1.1.

If female, subject must be:

- Pre-menarche and not sexually active, or
- Permanently surgically sterile (bilateral oophorectomy, bilateral salpingectomy or hysterectomy), or
- Practicing at least one of the following methods of birth control, on Study Day 1 (or earlier) through at least 30 days after stopping study drug (if not receiving RBV), or for up to 6 months after stopping study drug if receiving RBV (or as directed by local RBV label).
  - Progestogen-only hormonal contraception (injectable or implantable) associated with inhibition of ovulation, initiated at least 1 month prior to Study Day 1.
  - Bilateral tubal occlusion/ligation.
  - Vasectomized partner(s), provided the vasectomized partner has received medical assessment of the surgical success and is the sole sexual partner of the WOCBP trial participant.
  - Intrauterine device (IUD).
  - Intrauterine hormone-releasing system (IUS).
  - True abstinence: Refraining from heterosexual intercourse when this is in line with the preferred and usual lifestyle of the subject (periodic abstinence [e.g., calendar, ovulation, symptothermal, post-ovulation methods] and withdrawal are not acceptable).

Listed methods of contraception achieve a failure rate of less than 1% per year when used perfectly (consistently and correctly). For oral hormonal contraceptives, failure rates can increase up to 9% with typical use (including inconsistent or incorrect use).

Note: Contraceptive methods with low user dependency are implantable progesterone only hormonal contraception, IUD, IUS, bilateral tubal occlusion, and vasectomized partner.

If required per local practices, male or female condom with or without spermicide OR cap, diaphragm or sponge with spermicide should be used in addition to one of the birth control methods listed above (excluding true abstinence).

If male, subjects must be

- Prepubertal and not sexually active, or
- surgically sterile (vasectomy with medical assessment confirming surgical success), or
- have a female partner who is postmenopausal or permanently sterile (bilateral oophorectomy, bilateral salpingectomy or hysterectomy), or
- if sexually active with female partner(s) of childbearing potential must agree to practice contraception with a method listed below from Study Day 1 and for up to 9 months after stopping study drug (or as directed by the local RBV label if receiving RBV) or from Study Day 1 and continue for 120 days after last dose of study drug for subjects whose study regimen does not include RBV.
- Condom use in combination with one additional birth control method.
- True abstinence: Refraining from heterosexual intercourse – when this is in line with the preferred and usual lifestyle of the subject. (Note: Periodic abstinence [e.g., calendar, ovulation, symptothermal, post-ovulation methods] and withdrawal are not acceptable).

Additionally, male subjects must agree not to donate sperm from Study Day 1 through 120 days after the end of treatment if taking DAAs only, or for 9 months after the last dose of RBV (or per local RBV label).

### **5.3 Efficacy Pharmacokinetic, Pharmacogenetic and Safety Assessments/Variables**

#### **5.3.1 Efficacy and Safety Measurements Assessed and Flow Chart**

Study procedures described are listed in the following section of this protocol and are summarized in tabular format in [Appendix C](#).

##### **5.3.1.1 Study Procedures**

The study procedures outlined in [Appendix C](#) are discussed in detail in this section with the exception of the assessment of concomitant medications (Section [5.2.3](#)), and the collection of adverse event information (Section [6.1.4](#)). All study data will be recorded in the subject's source documentation and then on the appropriate eCRFs, with the exception of laboratory data which will be provided to the Sponsor electronically from the laboratory(ies).

##### **Informed Consent/Assent**

Signed study-specific informed consent and assent (as appropriate for age and country) will be obtained from the parent(s)/guardian(s) and subject before any study procedures are performed. If a subject becomes of legal age during the course of the study, the subject will need to be consented using the approved informed consent form. Details about how informed consent and assent will be obtained and documented are provided in Section [9.3](#).

##### **RBV Information**

Subjects taking RBV will be given the RBV Medication Guide (where applicable/locally available).

##### **Medical History**

A complete medical history, including history of tobacco, nicotine containing products and alcohol use, will be taken from each subject during the Screening Visit. An updated

medical history will be obtained prior to study drug administration and will serve as the baseline for clinical assessment.

### **Physical Examination**

A complete physical examination will be performed at visits specified in [Appendix C](#). A symptom-directed physical examination may be performed at any other visit, when necessary.

The physical examination performed on Study Day 1 will serve as the baseline physical examination for clinical assessment. Any significant physical examination findings after the first dose will be recorded as adverse events.

### **Vital Signs, Weight, Height and Waist Circumference**

Body temperature, blood pressure, pulse, body weight, height, and waist circumference will be measured at the visits specified in [Appendix C](#), or upon subject discontinuation. Blood pressure and pulse rate will be measured after the subject has been sitting for at least 3 minutes. The vital signs performed on Study Day 1 will serve as the baseline for clinical assessment. Height will be measured standing without shoes using a stadiometer. Waist circumference will be measured using a flexible tape at the level of the iliac crest at the end of expiration.

### **12-Lead Electrocardiogram**

The ECG obtained at Screening will serve as the baseline assessment. The ECG should be performed prior to blood collection. An ECG can be performed at subsequent visits if deemed clinically.

The ECGs will be evaluated by an appropriately trained physician at the site ("local reader"). The local reader from the site will sign, and date ECG tracings and will provide his/her global interpretation as a written comment on the tracing using the following categories:

- Normal ECG
- Abnormal ECG – not clinically significant
- Abnormal ECG – clinically significant

Only the local reader's evaluation of the ECG will be collected and documented in the subject's source. The automatic machine reading (i.e., machine-generated measurements and interpretation that are automatically printed on the ECG tracing) will not be collected.

### **Clinical Laboratory Tests**

Samples will be obtained at a minimum for the clinical laboratory tests outlined in [Table 8](#) at the visits indicated in [Appendix C](#).

An overview about the volume of blood drawn for each of the study visits is listed in [Appendix D](#) of this protocol. The Investigator/designee should refer to the local recommendations on blood drawn in pediatric patients (e.g., the guide on *"Ethical Considerations for Clinical Trials on Medical Products With the Paediatric Population"* or *"Blood Drawing For Human Subject Research"* by Duke University). The Investigator/designee should document exceptions to the local blood loss recommendations in the subject's source along with a justification as appropriate.

At the Study Day 1 visit, a blood sample is to be collected prior to the first dose of study drug which is to be administered during the visit. Subjects should be reminded to eat prior to their first dose of study drug after the sample is collected (e.g., suggest they bring a light snack). Fasting status will be recorded in the source documents and on the laboratory requisition. The baseline laboratory test results for clinical assessment for a particular test will be defined as the last measurement prior to the initial dose of study drug.

A certified central laboratory will be utilized to process and provide results for the clinical laboratory tests. Instructions regarding the collection, processing, and shipping of these samples will be provided by the central laboratory chosen for this study. The certified

laboratory chosen for this study is Covance. Samples will be sent to the following address:

North and South American sites:

Covance Central Laboratory Services  
[name]  
[name]  
[contact]  
[contact]

European sites:

Covance Central Laboratory Services  
[name]  
[name]  
[contact]  
[contact]

**Table 8. Clinical Laboratory Tests**

Hematology	Clinical Chemistry	Additional Tests
Hematocrit	Blood Urea Nitrogen (BUN)	HBsAg c
Hemoglobin	Creatinine	Anti-HCV Ab c
Red Blood Cell (RBC) count	Total bilirubin a,b	Anti-HIV Ab c
White Blood Cell (WBC) count	Direct and indirect bilirubin	FSH c
Neutrophils	Serum glutamic-pyruvic	Urine and Serum
Bands, if detected	transaminase (SGPT/ALT)	Human Chorionic
Lymphocytes	Serum glutamic-oxaloacetic	Gonadotropin (hCG) d
Monocytes	transaminase (SGOT/AST)	HCV RNA
Basophils	Alkaline phosphatase	IL28B c
Eosinophils	Sodium	HCV genotype and sub-genotype c
Platelet count (estimate not acceptable)	Potassium	Pharmacogenetic sample (optional)
ANC	Calcium	
Prothrombin Time/INR	Inorganic phosphorus	
Activated partial thromboplastin time (aPTT)	Uric acid	
Reticulocyte count	Cholesterol	
	Total protein	
	Glucose	
	Triglycerides	
	Albumin a	
	Chloride	
	Bicarbonate	
	Magnesium	
	Gamma-glutamyl transferase (GGT) a	
	Creatinine clearance (Cockcroft Gault calculation for subjects $\geq 12$ years old and Schwartz formula for those $< 12$ years old)	
	Alpha2-macroglobulin b	
	Haptoglobin b	
	Apolipoprotein A1 b	
Urinalysis		
Specific gravity		
Ketones		
pH		
Protein		
Blood		
Glucose		
Urobilinogen		
Bilirubin		
Leukocyte esterase		
Microscopic (reflex)		

- a. Also a component of the Child-Pugh Assessment.
- b. Also a component of FibroTest.
- c. Performed only at Screening. FSH will be taken for female subjects aged  $\geq 9$  to 17 years old.
- d. Serum and urine pregnancy testing only required for female subjects who are experiencing menses or are nearing sexual maturation in the opinion of the PI, or who are of child-bearing potential.

### **Acceptability Questionnaire**

For each subject who is taking the mini-tablet formulation, the parent(s)/guardian(s) of the subject will complete an Acceptability Questionnaire to provide feedback on the perception of the dosage form. The parent(s)/guardian(s) of the subject will be asked of their overall impression towards the dosage form and the administration via dosing

vehicle to the subject; such as duration of administration, volume of dosing vehicle, swallowability, and the convenience of administration.

The questionnaire will be completed at the visits as indicated in [Appendix C](#). The parent(s)/guardian(s) will indicate their answers on the questionnaire, which will be kept as part of the study record and copied into EDC by site personnel. Site personnel will encourage completion of the questionnaire at all applicable visits and will ensure that a response is entered for all items.

### **Pregnancy Test**

Females of non-childbearing potential (either pre-menarche and not sexually active or permanently surgically sterile as defined above in [Section 5.2.4](#)) at Screening do not require pregnancy testing. All female subjects who are experiencing menses or are nearing sexual maturation in the opinion of the Principal Investigator, or who are of child-bearing potential:

- A serum pregnancy test will be performed at the Screening visit only and analyzed by the central laboratory.
- Pregnancy testing will be performed as specified in [Appendix C](#) regardless of treatment regimen.
- Subjects that receive a RBV containing regimen will have pregnancy tests performed monthly throughout the Treatment Period and through Post-Treatment Week 16 or 4 months after the discontinuation of RBV, or according to the local RBV label and/or local treatment guidelines for RBV.
- Subjects receiving DAAs only should have urine pregnancy testing done through Post-Treatment Week 4.
- Urine pregnancy testing will be performed on-site during the study visit if there is a scheduled visit. The pregnancy result will be captured in the source document and recorded in the eCRF by site personnel. If there is not a scheduled study visit, subjects may either have pregnancy testing performed at the site as an unscheduled study visit or a urine pregnancy test may be conducted by the subject at home with a pregnancy test kit provided by the

site. If a urine pregnancy test is performed at home, site personnel should contact these female study subjects to capture the results of any study-related pregnancy tests in the source records only.

- If a urine pregnancy result is positive, a confirmatory hCG serum test should be collected and sent to the central lab.

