#### **6.1.6 Pregnancy**

Subjects and their partners should avoid pregnancy and males should avoid sperm donation throughout the course of the study, which is defined as from Study Day 1 until 30 days after the last dose of study drug if subjects do not take RBV, or from Study Day 1 until 6 months for WOCBP and 9 months for males after the last dose of the study drug containing RBV (or per local RBV label).

Pregnancy in a study subject must be reported to the AbbVie within 1 working day of the site becoming aware of the pregnancy. Subjects who report a positive pregnancy test during the Treatment Period must be notified to stop RBV (if applicable) immediately. Administration of DAAs may be continued at the investigator's discretion after discussion with the subject, if the benefit of continuing therapy is felt to outweigh the potential risk (as allowed per local guidance) (Section 5.4.1).

Information regarding a pregnancy occurrence in a study subject and the outcome of the pregnancy will be collected for pregnancies occurring up to 30 days after the end of treatment with DAAs only, or through Post-Treatment Week 28 (or per local RBV label) after the last dose of RBV for treatment with DAAs plus RBV. The investigator is encouraged to report the pregnancy information to the voluntary RBV Pregnancy Registry, if RBV is included within the regimen.

Subjects who discontinue study medications due to pregnancy will be monitored for SVR in the Post-Treatment Period as described in Section 5.4.1.

Pregnancy in a study subject is not considered an adverse event. However, the medical outcome of an elective or spontaneous abortion, stillbirth or congenital anomaly is considered a serious adverse event and must be reported to the Sponsor within 24 hours of the site becoming aware of the event.

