- j. A positive urine pregnancy test requires a confirmatory serum test. (Refer to Section 5.3.1.1 [Pregnancy Test] for additional details.) Females who are experiencing menses or are nearing sexual maturation in the opinion of the PI or who are of childbearing potential who are receiving RBV should have urine pregnancy testing done monthly starting from Day 1 (Baseline) through PT Week 16 after RBV discontinuation or per local label. Females who are experiencing menses or are nearing sexual maturation in the opinion of the PI or who are of childbearing potential who are receiving DAA only should have urine pregnancy testing done thru Post-Treatment Week 4.
- k. Non-cirrhotic subjects: Coagulation panel performed only at Day 1 and as clinically indicated.  
Cirrhotic subjects: Coagulation panel is required at all treatment visits.
- l. FSH for all female subjects aged  $\geq 9$  to 17 years old.
- m. Subjects with no history of cirrhosis who have not had a liver biopsy or Fibroscan within 24 months prior to screening, will have a screening FibroTest to determine the presence or absence of cirrhosis for the purpose of treatment assignment. Subjects who have a liver biopsy or FibroScan indicating cirrhosis at any time in the past will not need a Fibrotest to be performed at screening as evidence of cirrhosis.
- n. Perform a Fibrotest at Day 1 for any subject who did not have a FibroTest done during Screening.
- o. Applies only to subjects with cirrhosis. The Child-Pugh score will be calculated in the EDC RAVE system. Subjects who were considered to be non-cirrhotic at the Screening visit but identified as cirrhotic (according to definitions listed in Section 5.3.1.1) during the screening period will return to the site prior to the baseline visit for Child-Pugh assessment.
- p. HCC assessment for subjects with compensated cirrhosis only: Liver ultrasound will be performed at the screening visit. Liver ultrasound testing will occur yearly after Day 1.  
Subjects with a historical negative liver ultrasound, CT or MRI (within 3 months prior to screening) are not required to undergo a screening ultrasound.
- q. The local study drug labels and <http://www.hep-druginteractions.org/> should be utilized to evaluate concomitant medications for potential DDI.
- r. See specific information regarding the adverse event collection in Section 6.1.4.

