**Study Activities – Post-Treatment – Parts 1, 2 and 3**

Activity	Post-Treatment (PT)										Premature D/C	
	Post-Treatment Period of Parts 1 and 2 (PTP)				Part 3: Long-Term Follow-Up (LTFU)							
	PT Wk 4	PT Wk 12	PT Wk 24	PT Wk 36	PT Wk 48	PT Wks 96, and 144	PT Wks 96, and 144	PT Wks 96, and 144	PT Wks 96, and 144	PT Wks 96, and 144		
Vital Signs, Weight, Height, Waist Circumferences a	X	X	X	X	X	X	X	X	X	X	X	X
Urine Pregnancy Test b	X		(Weeks 12, 16)									X
Longitudinal Fibrotest			X							X c		
Hematology/Chemistry/Urinalysis d /Coagulation Panel	X											X
HCC Assessment: Liver Ultrasound e			X							X		X
Concomitant Medication Assessment f	X	X	X	X	X	X	X	X	X	X	X	X
Adverse Event Assessment g	X	X	X	X	X	X	X	X	X	X	X	X
HCV RNA Samples	X	X	X	X	X	X	X	X	X	X	X	X
HCV Resistance Sample h												
Tanner Pubertal Stage i		X					X			X j		X
Patient Reported Outcome k	X	X	X	X	X	X	X	X	X	X	X	X

D/C = Discontinuation

- Height and Waist circumference will be measured at PT Weeks 12, 36, 96 and 144 only.
- A positive urine pregnancy test requires a confirmatory serum test. (Refer to Section 5.3.1.1 [Pregnancy Test] for additional details.) Females who are experiencing menses or are nearing sexual maturation in the opinion of the PI or who are of childbearing potential who are receiving DAAs only should have urine pregnancy testing done thru Post-Treatment Week 4.  
 Females who are experiencing menses or are nearing sexual maturation in the opinion of the PI or who are of childbearing potential who are receiving RBV should have urine pregnancy testing done monthly starting from Day 1 (Baseline) through PT Week 16 after RBV discontinuation or per local label.

At the PT Visit 16 subjects may have an unscheduled office visit for pregnancy testing or elect to perform the tests at home with test kits provided by the site. Additional testing may be required per local RBV label.

- c. FibroTest will be performed at PT Weeks 24 and 144.
- d. Urinalysis will not be conducted after the Post-Treatment Week 4 visit.
- e. HCC assessment for subjects with compensated cirrhosis only: Liver ultrasound testing will occur yearly.
- f. Only medications taken for SAEs assessed as related to study drugs and treatment of HCV will be collected after 30 days post-dosing.

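### For girls on ribavirin, default pregnancy testing ends at Post-Treatment Week 16 or 4 months, about 8 to 12 weeks before the protocol's pregnancy-avoidance and pregnancy-collection periods end, unless the local label or guidelines require more

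*Protocol*

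**What the plan says.** The protocol sets three default end points for females who receive RBV.

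- **Testing.** Section 5.3.1.1 (Pregnancy Test) states: "Subjects that receive a RBV containing regimen will have pregnancy tests performed monthly throughout the Treatment Period and through Post-Treatment Week 16". The sentence goes on to allow 4 months after RBV stops, and then a further alternative: "or according to the local RBV label and/or local treatment guidelines for RBV". Appendix C, Treatment Period, note j asks for "urine pregnancy testing done monthly starting from Day 1 (Baseline) through PT Week 16 after RBV discontinuation or per local label". The note to the Urine Pregnancy Test row in the post-treatment table repeats this and adds: "At the PT Visit 16 subjects may have an unscheduled office visit for pregnancy testing or elect to perform the tests at home". It then says that the local RBV label may call for further tests.
- **Contraception and avoidance.** Section 5.2.4 sets contraception "for up to 6 months after stopping study drug if receiving RBV". Inclusion criterion 3 and exclusion criterion 1 use the same 6 months. Section 6.1.6 sets avoidance for women of childbearing potential to 6 months after the last RBV-containing dose. Each allows the local label instead.
- **Collection of pregnancy information.** Section 6.1.6 collects occurrence and outcome "through Post-Treatment Week 28 (or per local RBV label) after the last dose of RBV".

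Section 5.2.4 sends the site to Section 5.3.1.1 for testing. One section therefore sets 6 months of contraception and points to a default test schedule that ends at Week 16 or 4 months.

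The post-treatment row of Appendix C lists a urine test at Weeks 4, 12 and 16 and at premature discontinuation.

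**The concern.** The rationale under the inclusion criteria gives RBV's teratogenicity as the reason for the contraception and pregnancy-test criteria. The three end points therefore serve one risk, yet the step that would detect a pregnancy has the earliest default end. The protocol gives no reason for this.

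The testing alternatives are joined by a plain *or*. Nothing says that the longest applies, so a site that stops at Week 16 complies with the protocol.

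After that point little else is scheduled that would reveal a pregnancy. Pregnancy is not an adverse event under Section 6.1.6, and from 30 days after treatment Section 6.1.4 collects only serious events judged related to study drug. Under the defaults, pregnancy collection to Week 28 would then rest largely on the subject telling the site. What is at stake is subject safety and the completeness of pregnancy reporting.

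**Working it through.** The documents state no gap length, so there is no plan figure to reproduce. The check is calendar arithmetic.

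**Inputs**

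- End of default testing: Week 16 (Section 5.3.1.1, Appendix C) or 4 months (Section 5.3.1.1).
- End of avoidance: 6 months (Sections 5.2.4 and 6.1.6, inclusion criterion 3, exclusion criterion 1).
- End of collection: Week 28 (Section 6.1.6).
- One calendar month = 365.25 / 12 / 7 = 4.348 weeks, so 4 months = 17.39 weeks and 6 months = 26.09 weeks.

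**Gap = end of period − end of default testing**

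| Testing ends | Period ends | Gap (weeks) |
|---|---|---|
| Week 16 | 6 calendar months | 26.09 − 16 = 10.1 |
| Week 16 | Week 28 | 28 − 16 = 12.0 |
| 4 calendar months | 6 calendar months | 26.09 − 17.39 = 8.7 |
| 4 calendar months | Week 28 | 28 − 17.39 = 10.6 |
| Week 16 | six 4-week months | 24 − 16 = 8.0 |
| Local label covers the full period | any | 0 |

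Pairing 4 calendar months with six 4-week months would give 24 − 17.39 = 6.6 weeks, but that mixes two conventions and is not used. The avoidance and collection end points themselves differ by 28 − 26.09 = 1.9 weeks.

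**As a share of the period**

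- Post-treatment part only, from a Week 16 cut-off: 10.09 / 26.09 = 39% to 6 months, and 12 / 28 = 43% to Week 28.
- Section 6.1.6 starts avoidance at Study Day 1. Over that whole period the share is 10.09 / (12 + 26.09) = 26% for 12-week treatment and 10.09 / (24 + 26.09) = 20% for 24-week treatment.

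**Comparison with the regimens without RBV**

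For girls on direct-acting antivirals alone, testing runs through Post-Treatment Week 4 (28 days), and avoidance and collection end at 30 days. The difference is 2 days, so the wide separation appears only in the RBV regimens.

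**Row against note in Appendix C**

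Monthly testing to Week 16 implies Weeks 4, 8, 12 and 16. The row lists 4, 12 and 16. Week 8 is not a visit column, but neither is Week 16, which the row does list.

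**The case against.** The strongest reply is that the documents contain no impossibility. Contraception, testing and pregnancy reporting are different activities, no passage requires them to end together, and a site can comply with all three. Every passage also defers to the local RBV label, and the post-treatment note in Appendix C provides for further tests under it. The true gap depends on a label that the documents do not give. This stands, and it limits the point to the defaults. It does not remove the point: the same deferral is attached to the 6-month and Week 28 figures, so it cannot explain why the stated defaults differ.

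Four stronger readings are tempting, and the documents do not support them.

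- *Testing stops at Week 16 and the rest of the period has no test.* This ignores the 4-month and local-label alternatives in the same sentence of Section 5.3.1.1.
- *There is an 8-week hole between Weeks 4 and 12.* The row's own note requires monthly tests, and Section 5.3.1.1 covers months without a visit through an unscheduled visit or a home kit. The table was also read by machine. At most, the row omits a month that its note already requires.
- *Exposed pregnancies would be missed.* This is not shown. Subjects return at Post-Treatment Weeks 24 and 36, and sites must report a pregnancy within 1 working day of learning of it.
- *The amendment extended contraception and overlooked testing.* The change log shows female contraception moving from 4 to 6 months, which is suggestive. But the superseded Section 6.1.6 already used Week 28 for women of childbearing potential while contraception stood at 4 months, so the periods differed before. The log is background only.

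**Conclusion.** The point holds for the protocol's defaults. For females on RBV, no pregnancy test is scheduled for about the last 8 to 12 weeks of the avoidance and collection periods unless the local RBV label or local guidelines require it. The figure depends on how months are counted and on which default end of testing a site uses. Across local labels the range is 0 to 12 weeks. The shares of 39% and 43% describe the post-treatment part only and should not be read as shares of the whole avoidance period.

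The subjects concerned are females who are menstruating, nearing maturation or of childbearing potential and who receive RBV, that is, those with genotype 1 non-b or genotype 4 infection. The documents give neither the split by sex nor the split by subtype, so no head-count is offered.

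This is a matter of subject safety and pregnancy reporting. It affects no efficacy endpoint or planned analysis. The mismatch between row and note in Appendix C is secondary.

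**What to change.** Reconcile Section 5.3.1.1 (Pregnancy Test) and the two Appendix C notes with inclusion criterion 3, exclusion criterion 1, Section 5.2.4 and Section 6.1.6. There are two ways to do this:

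- align the default end points of testing, avoidance and collection; or
- keep them different, state why, and state how the local-label alternative applies to each, including which alternative governs when they disagree.

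Make the post-treatment Urine Pregnancy Test row match the monthly rule in its note. The sponsor decides the duration; this review does not say which of the present figures is right.

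The cost is protocol wording and one schedule row. If the sponsor chose to test for longer, the added burden would be at most a few more home urine kits and site calls for a small number of girls. Section 5.3.1.1 already provides for home kits with site follow-up, and Post-Treatment Week 24 is already a scheduled visit.
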